Appendix I: Moderate Tricuspid Regurgitation Trial Echocardiographic Image Acquisition Protocol

General Considerations:

- For the echocardiogram, the patient will be positioned in left lateral recumbency or in the position that permits optimal imaging. All images should be acquired during quiet respiration unless otherwise specified.
- At least 3 and no more than 5 cardiac cycles are requested for two-dimensional imaging unless otherwise specified. At least 5 cardiac cycles are required for spectral pulsed wave (PW) and continuous wave (CW) Doppler. For patients in atrial fibrillation, a minimum of 2 captures of 5 consecutive cardiac cycles are required. Unless otherwise specified, depth should be adjusted to maximize the image while including all necessary structures. Harmonic imaging should be employed to optimize visualization of endocardial borders.
- All PW, CW Doppler and m-mode recordings will be performed at a sweep speed of 100 mm/sec. Gain should be adjusted to reduce excess noise. Color Doppler Nyquist limits will be adjusted to the range of 50-70 cm/sec, unless otherwise specified. The following protocol is required however additional images should be obtained at the discretion of the sonographer/physician.

I. Protocol for Transthoracic Echocardiogram (TTE) pre and post-surgery

1. Parasternal long axis
 - 2D image
 - Color Doppler across aortic and mitral valves
 - Zoom image of LVOT
 - Zoom image of vena contracta
2. Parasternal right ventricular inflow view of the tricuspid valve
 - 2D image include RV and RA (optimize endocardium)
 - Color Doppler across tricuspid valve (TV) including distal jet into RA
 - Zoom view of TV annulus (for measurement of TV annulus)
 - Zoom view of vena contracta proximal jet of TR
 - Zoom view of the proximal flow convergence region of the TR jet after baseline shifted downward (same direction as TR jet flow) to a Nyquist of 25-35 cm/s
 - Continuous wave Doppler across TV valve to estimate TV gradient.
3. Parasternal outflow view of the pulmonic valve
 - 2D
 - Color Doppler across PV

- Pulse wave Doppler
- CW of the pulmonary valve
- Zoom 2D image of pulmonary valve annulus for measurement of the pulmonary annular diameter.

4. Basal PSAX (at the aortic valve level)

- 2D image include TV, short axis of aortic valve and RVOT
- Color Doppler of TV include distal jet into right atrium
- Zoom view of Color Doppler view of vena contracta of TR

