- Zoom view of the proximal flow convergence region of the TR jet after baseline shifted downward (same direction as TR jet flow) to a Nyquist of 25-35 cm/s
- Pulsed Doppler sample of pulmonary flow at the level of the pulmonary valve to measure pulmonary velocity time interval (VTI) opening and closing transients of the pulmonary valve should be recorded.

5. PSAX of ventricles: ensure on-axis views and include right ventricle

- Level of the mitral valve when both anterior and posterior leaflets are visualized.
- Mid-papillary muscle level.
- Level of the apex

6. Apical 4-chamber view

- Full sector to include all four chambers
- Focus on right heart: 2D to Include RV and RA, making sure to include lateral wall of RV (often requires a slight medial tilt of transducer)
- Zoom view of RV only (include base of RV/TV annulus and optimize RV endocardium)
- Color Doppler across TV one including right atrium to capture the distal jet taking care to include wall-impinging eccentric jets in the region of interest.
- Zoom view of TV annulus (for measurement of TV annulus)
- Zoom view of Color Doppler across TV to image the vena contracta of the TR jet
- Zoom view of the proximal flow convergence region of the TR jet after baseline shifted downward (same direction as TR jet flow) to a Nyquist of 25-35 cm/s
- PW of TV at leaflet tips and at level of TV annulus
- CW of TV for estimation of pulmonary artery systolic pressure
- M-mode across lateral tricuspid annulus (for TAPSE measurement)
- Tissue Doppler of lateral tricuspid annulus (to measure peak annular velocity)
- Focus on left heart:

- 2D include both LV and LA
- Zoom view of LV only (avoid foreshortening of LV apex)
- Color Doppler across MV one including left atrium to capture the distal jet taking care to include wall-impinging eccentric jets in the region of interest.
- Zoom view of MV annulus (for measurement of MV annulus)
- -Zoom view of the proximal flow convergence region of the MR jet after baseline shifted downward (same direction as MR jet flow) to a Nyquist of 30-40 cm/s
- PW of MV at leaflet tips and at level of MV annulus
- PW Doppler of right pulmonary vein flow. The sample volume should be placed at least 1 cm within the pulmonary vein
- CW of MV
- Tissue Doppler of lateral and septal mitral annulus

7. Apical 5-Chamber view

- Color flow Doppler across LVOT/Aortic valve

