5.2.2 Echocardiography

All echocardiography outcomes are measured by transthoracic 2D echocardiography unless otherwise noted

- Degree of TR at index hospital discharge
- Degree of TR at 12 and 24 months
- RV size at 12 and 24 months
- RV function (normal, mildly impaired, moderately impaired, severely impaired, peak tricuspid annular velocity, TAPSE, RVFAC) at 12 and 24 months
- Pulmonary artery pressure at 12 and 24 months
- RV volume at 12 and 24 months as measured by transthoracic 3D echocardiography

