6.2.3 Missing Secondary Outcomes Data

In general, missing outcome values for secondary endpoints will not be imputed and analyses will be based on all available data. Multiple imputation may be used for specific analyses (e.g., cost analysis).

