6.5.2.2 Echocardiography

Degree of TR: The distribution of the degree of TR at hospital discharge, 12, and 24 months will be presented for each randomization arm and compared using chi-squared tests. Between group differences in TR progression defined as presence of severe TR at 24 months, or for patients enrolled with less than moderate TR, progression by two grades compared to baseline will be compared using a two-tailed 0.05 level chi-squared test.

Additional echo parameters: RV size, RV function (normal, mildly impaired, moderately impaired, severely impaired, peak tricuspid annular velocity, TAPSE, RVFAC), and pulmonary artery pressure at 12 and 24 months will be compared between groups. RV volume as assessed by 3D TTE at 12 and 24 months will be compared between groups. Continuous variables will be compared for between group differences using the Wilcoxon Rank Sum test, and the level of function by chi-square test.

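### Pulmonary artery pressure is read from the tricuspid jet that annuloplasty is meant to reduce, so the planned available-case comparison is conditional on a post-randomization variable

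*SAP*

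**What the plan says.** Both documents list pulmonary artery pressure at 12 and 24 months as a secondary endpoint. SAP 5.2.2 sets the modality: "All echocardiography outcomes are measured by transthoracic 2D echocardiography unless otherwise noted". No invasive measurement is planned.

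The source of the value is in Protocol Appendix I. The right ventricular inflow view calls for "Continuous wave Doppler across TV valve to estimate TV gradient", and the apical 4-chamber view calls for "CW of TV for estimation of pulmonary artery systolic pressure". Among the variables to be measured (Appendix I, section III), RVSP is the only pressure. The basal short-axis view also records "Pulsed Doppler sample of pulmonary flow at the level of the pulmonary valve", but neither document names this as a source or fallback for pulmonary artery pressure.

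For the analysis, SAP 6.5.2.2 lists RV size, RV function "and pulmonary artery pressure at 12 and 24 months will be compared between groups", and it names the test: "Continuous variables will be compared for between group differences using the Wilcoxon Rank Sum test". Under SAP 6.1 the level is two-sided 0.05. On missing values, SAP 6.2.3 says that, in general, "missing outcome values for secondary endpoints will not be imputed and analyses will be based on all available data". It then adds an option: "Multiple imputation may be used for specific analyses (e.g., cost analysis"). The only imputation model that is specified (SAP 6.5.1.3) is for the primary endpoint.

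**The concern.** Whether a patient has an RVSP value is settled after randomization, by whether there is enough regurgitation to measure. The randomized procedure is intended to change exactly that. The TR scale includes a none/trace category, so some patients at follow-up may have little or no jet.

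When those patients are left out, the two groups compared are no longer the randomized groups. If jets are measurable less often in one arm, and patients with a measurable jet differ in pressure from those without, the test can show a difference where none exists or hide one that does. Right heart performance is a named secondary aim, and the protocol says the secondary analyses are there to help interpret the trial. A misleading pulmonary pressure result would feed into that interpretation. Neither document says what is recorded when no adequate jet is present, and neither plans a sensitivity analysis for this endpoint.

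**Working it through.** **What the documents supply.** They give the Doppler source, the available-case default, the Wilcoxon test, two-sided 0.05, and 400 patients randomized 1:1. They give no SD, power or expected missing rate for pulmonary artery pressure, so there is no stated figure to reproduce for this endpoint. The stated power of about 90% belongs to the primary endpoint (25% vs 12%) and is not in dispute: 200 per arm gives 92.0% by the pooled chi-squared formula.

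**Assumptions (not in the documents).**
- 180 echos per arm (90% of 200).
- True pressure X is Normal with mean 38 and SD 11 mmHg in both arms, so there is no true difference.
- P(jet measurable | X) = expit(a + b·(X − 38)/11). The intercept a is solved in each arm to give the stated percentage measurable.
- b = 0.3, 0.5 or 0.8, that is, odds multiplied by 1.35, 1.65 or 2.2 per SD of pressure.

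**Formulas.** False difference d = E[X | measurable, repair] − E[X | measurable, control]. SE = 11·√(1/n₁ + 1/n₂), where n is 180 × the proportion measurable. Rejection = Φ(−1.96 + d/SE) + Φ(−1.96 − d/SE). This is a normal approximation to the planned test.

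**One case in full: 85% vs 60% measurable, b = 0.5.**
- Intercepts: a = 1.819 (control) and 0.429 (repair).
- Observed means: 38.80 and 40.08, so d = 1.28 mmHg.
- n = 153 and 108, so SE = 11·√(1/153 + 1/108) = 1.38.
- d/SE = 0.93, so rejection = Φ(−1.03) + Φ(−2.89) ≈ 15%.

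**All cases with the same slope in both arms.**

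| Measurable, control vs repair | False difference (mmHg) at b = 0.3 / 0.5 / 0.8 | Rejection at nominal 5% |
|---|---|---|
| 85% vs 80% | 0.16 / 0.26 / 0.38 | 5.2% / 5.5% / 6.0% |
| 85% vs 72% | 0.42 / 0.67 / 0.98 | 6.2% / 8.0% / 11.6% |
| 90% vs 75% | 0.48 / 0.78 / 1.15 | 6.6% / 9.3% / 14.6% |
| 85% vs 60% | 0.80 / 1.28 / 1.88 | 8.9% / 15.3% / 27.4% |
| 85% vs 50% | 1.13 / 1.80 / 2.64 | 12.0% / 23.3% / 43.8% |

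With b = 0 in both arms the false difference is zero and rejection is 5%, whatever the percentages.

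**Different slopes, 85% vs 60%.** With b = 0.5 in controls and 0 in repair, the means are 38.80 and 38.00, so d = −0.80 mmHg, the opposite sign. With b = 0.5 and 0.2, the means are 38.80 and 38.87, so d is about +0.1.

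**Cross-check with the rank-sum test itself.** A simulation of 2,000 trials per scenario (180 per arm, SD 12) gave 14.5% rejection at 85% vs 60% with b = 0.5, in line with the 15% above. Where measurability was equal, or unrelated to pressure, rejection stayed between 0.04 and 0.06. Steeper slopes gave more: at 85% vs 60%, 39% for b = 1.0 and 58% for b = 1.5. The table is therefore a range for moderate slopes, not a ceiling.

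**The case against.** The strongest reply is that the mechanism is documented but the bias is not. Several parts of it stand.

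- **No measurability rate is given.** A reader might infer that RVSP will be missing more often after repair. The documents do not say so, nor what quality of jet is needed; a patient with mild or trace TR may still have a usable signal. The 25% vs 12% hypothesis concerns a composite of death, reoperation and TR failure, not presence of a jet. Controls can also lack a jet: none/trace TR with annular dilation is an entry route, and the protocol's background accepts that TR resolves in some patients after left-sided correction alone. If the 13-point gap is borrowed purely as an illustration (85% vs 72%), the false difference is only 0.4 to 1.0 mmHg.
- **Direction is open.** A reader might infer that the comparison is tilted against repair. That follows only if the slope is the same in both arms. After annuloplasty, a residual jet may reflect the repair result more than the pressure, and the sign can then reverse.
- **The selected group need not be small.** Even the widest gap in the table leaves half the repair arm measurable, so the repair patients compared should not be called a minority.
- **The SAP leaves room.** SAP 6.2.3 is a general rule with optional imputation, SAP 6.1 allows more appropriate methods if a planned one proves unsuitable, and it already lists the number of non-missing values for continuous variables. TR grade by arm is also reported.

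The last point does not close the gap. None of these provisions specifies anything for this endpoint. A count of non-missing values does not separate absence of a jet from absence of an echo. Imputation that assumes missing at random would not by itself deal with values missing because there is no jet.

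**Conclusion.** The concern holds in conditional form. As planned, the pulmonary artery pressure comparison is made among patients with a measurable TR jet, and having one is a post-randomization variable that the procedure is intended to affect. Bias needs two things together: measurability that differs by arm and a link between measurability and pressure. The documents establish neither and determine neither size nor sign.

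The range from 0.2 mmHg to 2.6 mmHg rests entirely on the assumed sample, SD, percentages and common slope. It shows that the effect can be anything from negligible to serious, and does not predict where this trial will fall.

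A reader might go further and conclude that RVSP must be replaced as the endpoint. The documents do not support that. The pulmonary-valve Doppler is acquired for a velocity time measurement, and nothing in either document establishes it as a substitute for pulmonary artery systolic pressure. This is a low-cost improvement to one secondary endpoint among many, and the primary analysis does not depend on it.

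**What to change.** Revise SAP 6.5.2.2, which the SAP allows up to data lock:

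1. State that pulmonary artery pressure is RVSP from tricuspid continuous-wave Doppler, and have the Core Lab code an echo without a measurable TR jet separately from a missing echo.
2. Report the number and percentage measurable by arm at 12 and 24 months.
3. Label the Wilcoxon result as conditional on a measurable jet and not as a randomized comparison.
4. Add a bounding or tipping-point sensitivity analysis. In each arm the full mean is p·m(observed) + (1 − p)·m(unmeasured). Vary m(unmeasured) separately by arm over a pre-stated range, and report where the conclusion changes.
5. Optionally, as a supportive analysis only and if the Core Lab considers it valid, add a jet-independent measure from the pulmonary-valve pulsed Doppler already acquired, without replacing the endpoint.

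The cost is a little more Core Lab coding and analysis, plus a more cautious conclusion about pulmonary artery pressure. Steps 1 to 4 need no new imaging.

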6.5.2.3 Quality of life

QOL will be measured using the KCCQ, SF-12, and EQ-5D. We will employ two

approaches to the analysis of QOL. The first will be to base the analysis on longitudinal mixed effects models. These models would predict outcome from treatment group and time. The mixed modeling approach requires an assumption that patient dropout is ignorable in that the probability of dropping out at any time is related only to previously observed data. Of course, this assumption may not hold, and moreover it is impossible to test robustly from the data at hand. An alternative approach, not subject to this criticism, will be to separate the data into strata defined by the time of death or dropout. We will then estimate a separate linear model, including a treatment effect, for the data in each stratum. This method, known as pattern-mixture modeling, is not sensitive to un-testable assumptions about the dropout mechanism because it models the data directly in strata defined by dropout time. The method of Wu and Bailey is an instance of pattern-mixture modeling (Wu & Bailey, 1989).

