Six Minute Walk and Gait Speed Tests: Differences between groups in gait speed and the distances travelled during the 6MWT will be compared using the Wilcoxon Rank-Sum test. We will also assess the extent to which changes over time (in gait speed and distance walked) are related to other outcomes.

Additional echo parameters: RV function (normal, mildly impaired, moderately impaired, severely impaired, peak tricuspid annular velocity, TAPSE, RVFAC) at 12 and 24 months and pulmonary artery pressure at 12 and 24 months will be compared between groups. RV volume as assessed by 3D TTE at 12 and 24 months will be compared between groups. Continuous variables will be compared for between group differences using the Wilcoxon Rank Sum test, and the level of function by chi-squared test.

Quality of life: QOL will be measured using the KCCQ, SF-12, and EQ-5D. We will employ two approaches to the analysis of QOL. The first will be to base the analysis on longitudinal mixed effects models. These models would predict outcome from treatment group and time. The mixed modeling approach requires an assumption that patient dropout is ignorable in that the probability of dropping out at any time is related only to previously observed data. Of course, this assumption may not hold, and moreover it is

impossible to test robustly from the data at hand. An alternative approach we will also use, not subject to this criticism, will be to separate the data into strata defined by the time of death or dropout. We will then estimate a separate linear model, including a treatment effect, for the data in each stratum. This method, known as pattern-mixture modeling, is not sensitive to un-testable assumptions about the dropout mechanism because it models the data directly in strata defined by dropout time. The method of Wu and Bailey is an instance of pattern-mixture modeling.

Adverse Events: Differences in the incidence of individual AEs within 24 months post-randomization will be compared between randomization arms using Poisson regression. Ninety-five percent confidence intervals (based on the Poisson distribution) for the risk ratios for individual AEs for treatment with MVS and TV annuloplasty versus MVS alone will be computed.

NYHA classification: The distribution of NYHA at 12 and 24 months will be presented for each randomization arm and compared using a chi-squared test.

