5.2.3 Quality of Life

- SF-12 at 6, 12, 18 and 24 months post-randomization.
- KCCQ at 6, 12, 18 and 24 months post-randomization.
- EQ-5D at 6, 12, 18 and 24 months post-randomization.

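### The pattern-mixture analysis of quality of life moves the untestable dropout assumption rather than removing it, and as written it ends at stratum effects that no step combines into one between-arm contrast

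*SAP*

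**What the plan says.** SAP 5.2.3 schedules three QOL instruments at the same four visits, for example "KCCQ at 6, 12, 18 and 24 months post-randomization". SAP 6.5.2.3 plans two analyses.

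The first is a longitudinal mixed model: "These models would predict outcome from treatment group and time". The SAP says that this model needs dropout to be ignorable, and concedes that "this assumption may not hold, and moreover it is impossible to test robustly from the data at hand".

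The second is offered as the answer to that concession: "An alternative approach, not subject to this criticism, will be to separate the data into strata defined by the time of death or dropout". Then: "We will then estimate a separate linear model, including a treatment effect, for the data in each stratum". The SAP says that this approach "is not sensitive to un-testable assumptions about the dropout mechanism because it models the data directly in strata defined by dropout time", and adds: "The method of Wu and Bailey is an instance of pattern-mixture modeling".

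The Protocol (Analyses of Secondary Endpoints, Quality of life) has the same plan and the same claim: "This method, known as pattern-mixture modeling, is not sensitive to un-testable assumptions about the dropout mechanism".

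Neither text gives a rule for QOL after dropout, a step that combines the strata, or a QOL contrast at a named time point. SAP 6.2.3 says that missing secondary outcomes will in general not be imputed.

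**The concern.** There are three linked problems.

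1. A stratum whose patients leave before 24 months holds no data on later visits. Anything said about those visits rests on extrapolation or on borrowing from another pattern, and the data cannot test either. The SAP faults the mixed model for relying on an untestable assumption, then presents as free of that fault a method that relies on another one.
2. Time of death or dropout is settled after randomization and may depend on treatment. Within a stratum the arms are selected groups, so a stratum effect is not a randomized comparison, and no step is written that returns to one.
3. Death and dropout share one stratum definition. After dropout QOL exists but is unseen; after death it is undefined.

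This is the only check planned on the mixed model's dropout assumption. It applies to three self-reported instruments in an open-label trial (SAP 3.1.2). Agreement between the two analyses could be read as assumption-free confirmation, which it would not be.

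**Working it through.** The documents give no QOL dropout rate, SD, effect size or power, so there is no planned figure to reproduce. Every rate, SD and shift below is an assumption.

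**Step 1. What each stratum contains.** Visits are from SAP 5.2.3; the baseline assessment is from the Protocol's Data Collection Schedule.

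| Last QOL visit | Follow-up visits seen | Not seen up to 24 months |
|---|---|---|
| Baseline | none | 6, 12, 18, 24 |
| 6 months | 6 | 12, 18, 24 |
| 12 months | 6, 12 | 18, 24 |
| 18 months | 6, 12, 18 | 24 |
| 24 months | all | none |

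Only the last row has 24-month data. In the first row no follow-up effect can be estimated at all.

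**Step 2. The same observed data, different overall effects.** Let d1 and d0 be the dropout proportions with annuloplasty and with mitral surgery alone. Let s1 and s0 be the unseen 24-month mean of dropouts minus the completer mean in the same arm.

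Arm mean = (1 − d) × completer mean + d × (completer mean + s) = completer mean + d × s.

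Overall effect = completer effect + d1·s1 − d0·s0.

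Take a completer effect of 0, d1 = 0.10 and d0 = 0.15:

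| Unseen shift | In both arms | Annuloplasty arm only | Control arm only |
|---|---|---|---|
| −10 | −1.0 + 1.5 = +0.5 | −1.0 | +1.5 |
| −20 | −2.0 + 3.0 = +1.0 | −2.0 | +3.0 |

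Nothing observed differs between the cells, yet the overall effect runs from −2.0 to +3.0. The data cannot choose between them.

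**Step 3. Stratum effects when the true effect is zero.** Assume a 24-month score with SD 20, and a normal dropout propensity that rises as health falls. Score and propensity each load 0.7 on health, so they correlate at −0.7 × 0.7 = −0.49, and 20 × 0.49 = 9.8. Let φ be the standard normal density at the cut-off for dropout proportion d. Relative to the arm mean, completers average +9.8·φ/(1 − d) and dropouts −9.8·φ/d.

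- Control, d = 0.15, φ = 0.2332: completers +2.69, dropouts −15.23.
- Annuloplasty, d = 0.05, φ = 0.1031: completers +1.06, dropouts −20.21.
- Completer effect −1.62 from unrounded values (simulated −1.59); dropout effect −4.98 (simulated −5.05).
- Average of the two effects with pooled shares: 0.90 × (−1.62) + 0.10 × (−4.98) = −1.96 (simulated −1.94).
- Average with each arm's own shares: annuloplasty 0.95 × 1.064 − 0.05 × 20.21 = 0; control 0.85 × 2.688 − 0.15 × 15.23 = 0. The difference is 0, the truth.

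At 15% v 10% the simulated stratum effects are −0.8 and −2.0, with a pooled-share average of −0.9. At 15% v 15% with the same mechanism they are about 0. The dropouts' 24-month values used here would not be seen in the trial. Even with them, stratum effects and their pooled average miss the truth. Arm-specific means with arm-specific proportions recover it.

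**Step 4. Size at different dropout levels.** Simulations with no true effect, random-intercept SD 15, residual SD 10, the four visits, and logistic dropout on QOL:

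| Dropout in the two arms | QOL-related in | Spurious completer difference |
|---|---|---|
| 7% v 6% | both arms | about 0.2 |
| 14% v 9% | both arms | about 0.5 |
| 20–24% v 10% | the higher-dropout arm only | about 2.4 to 3.4 |

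The arm that loses more low-QOL patients looks better among completers. The last row depends on how steeply dropout follows QOL: at 24% v 10%, varying that steepness gave 1.6 to 4.0.

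**The case against.** The strongest defence is the SAP's own qualifier. It speaks of assumptions about the dropout mechanism, and a pattern-mixture model indeed needs no model for the probability of dropout. Read that narrowly, the phrase is defensible. What does not stand is the inference drawn from it, that the method escapes the criticism made of the mixed model. A reader might go further and call the sentence false in every sense; the qualifier does not support that.

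The SAP also names an established method as an instance, and a combining step might be meant by it. The cited source cannot be consulted here, and naming an instance does not specify a procedure. The safe statement is that no combining step is written, not that none was intended.

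The consequence is limited. The mixed model still gives an overall comparison with its assumption openly stated. Mortality has its own analysis (SAP 6.5.2.4), though that does not settle how deaths enter the QOL strata. SAP 6.5.1.3 expects few patients to be missing the primary endpoint. The Protocol excludes patients unlikely to comply with follow-up and those with life expectancy under two years. None of this fixes a QOL dropout rate, but it gives no support for assuming a high one.

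A reader might also take smaller effects in early-dropout strata as proof of selection bias. That does not follow, because those strata end at earlier visits. In a simulation with a benefit growing linearly to 5 points, the stratum effects were 1.15, 2.29, 3.34 and 4.87 against true values at the same visits of 1.25, 2.5, 3.75 and 5. Most of the spread was the growing effect; selection moved the estimates by about 0.1 to 0.4 points.

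**Conclusion.** The concern holds. The claimed freedom from untestable assumptions does not exist for any statement about QOL after dropout, and the written analysis stops at effects within strata formed after randomization, with death and dropout pooled.

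The size is unknown because it turns on dropout rates that the documents do not give. Under the assumptions above, the spurious completer difference is about 0.2 to 0.5 points with low to moderate dropout that is QOL-related in both arms. It is about 2.4 to 3.4 points in an extreme case with dropout at 20–24% v 10% and QOL-related in one arm only. With similar dropout rates and mechanisms in both arms it is near zero.

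Two further inferences are not supported. The primary conclusion is not at risk: QOL is secondary and the primary endpoint has its own missing-data method. Nor does the SAP set a 24-month QOL effect as its target; 24 months is simply the last QOL visit, and the missing target is part of the same gap.

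**What to change.** In SAP 6.5.2.3 and the matching Protocol paragraph:

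- Delete both statements that the method escapes untestable assumptions. Say instead that it replaces a model for dropout with an assumption about unseen QOL.
- Name the QOL contrast and its time point, for example the between-arm difference at 24 months.
- State an identifying restriction for unseen visits, and vary it as a sensitivity analysis, for example over a range of delta shifts that may differ by arm.
- Average arm-specific stratum means over each arm's own pattern proportions to give one between-arm contrast, with a variance that includes the estimation of those proportions.
- Say how death is handled, separately from dropout.

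The cost is wording and modest programming. The small downside is that a restriction must be chosen, defended and varied.
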